### **3.11.3.3 Visit 5 (Week 8)**

The following procedures/assessments will be performed at visit 5 (week 8):

- physical examination symptom directed
- clinical laboratory tests
- anti-dsDNA Ab, C3, and C4 only
- vital signs measurements (includes systolic and diastolic blood pressures, pulse, and temperature)
- urine pregnancy test on all women regardless of childbearing potential
- concomitant medication review
- adverse event inquiry
- SLEDAI-2K
- BILAG-2004
- 28-joint count examination for pain and tenderness
- SFI
- PhGA
- C-SSRS Since Last Visit version
- access eCRF page for treatment allocation.
- study drug administration after all assessments have been completed. (Patients should be monitored, at the discretion of the investigator, for at least 1 hour after study drug administration.)

### **3.11.3.4 Visit 6 (Week 12)**

The following procedures/assessments will be performed at visit 6 (week 12):

- physical examination symptom directed
- clinical laboratory tests
- ANA
- anti-dsDNA Ab, C3, and C4
- anti-U1-70K snRNP Ab, anti-Sm Ab, CRP, IgG, IgM, IgE, IgA

- anti–IPP-201101 Ab
- vital signs measurements (includes systolic and diastolic blood pressures, pulse, and temperature)
- urine pregnancy test on all women regardless of childbearing potential
- concomitant medication review
- adverse event inquiry
- SLEDAI-2K
- BILAG-2004
- 28-joint count examination for pain and tenderness
- SFI
- SF-36
- PhGA
- FACIT-Fatigue
- C-SSRS Since Last Visit version
- access eCRF page for treatment allocation.
- study drug administration after all assessments have been completed. (Patients should be monitored, at the discretion of the investigator, for at least 1 hour after study drug administration.)

### **3.11.3.5 Visits 7 and 8 (Weeks 16 and 20)**

The following procedures/assessments will be performed at visits 7 and 8 (weeks 16 and 20, respectively):

- physical examination symptom directed
- clinical laboratory tests
- anti-dsDNA Ab, C3, and C4 only
- anti–IPP-201101 Ab (visit 8, week 20)
- vital signs measurements (includes systolic and diastolic blood pressures, pulse, and temperature)
- urine pregnancy test on all women regardless of childbearing potential
- concomitant medication review
- adverse event inquiry
- SLEDAI-2K
- BILAG-2004
- 28-joint count examination for pain and tenderness
- SFI
- PhGA
- C-SSRS Since Last Visit version
- access eCRF page for treatment allocation.

- study drug administration after all assessments have been completed. (Patients should be monitored, at the discretion of the investigator, for at least 1 hour after study drug administration.)

In addition, a blood sample (5 mL) will be obtained for measurement of IPP-201101 plasma concentration prior to and 5 minutes and 1, 2, and 24 hours after study drug administration at visit 7 (week 16) from patients at selected North American and Western European study centers. The actual dates and times of study drug administration and the date and time of sampling will be recorded on the CRF.

### **3.11.3.6 Visit 9 (Week 24)**

The following procedures/assessments will be performed at visit 9 (week 24):

- physical examination symptom directed
- clinical laboratory tests
- ANA
- anti-dsDNA Ab, C3, and C4
- anti-U1-70K snRNP Ab, anti-Sm Ab, CRP, IgG, IgM, IgE, IgA
- vital signs measurements (includes systolic and diastolic blood pressures, pulse, and temperature)
- urine pregnancy test on all women regardless of childbearing potential
- concomitant medication review
- adverse event inquiry
- SLEDAI-2K
- BILAG-2004
- 28-joint count examination for pain and tenderness
- SFI
- SDI
- SF-36
- PhGA
- FACIT-Fatigue
- C-SSRS Since Last Visit version
- In vitro intracellular and secreted cytokine response
- Access eCRF page for treatment allocation.
- study drug administration after all assessments have been completed. (Patients should be monitored, at the discretion of the investigator, for at least 1 hour after study drug administration.)

### **3.11.3.7 Visits 10 and 11 (Weeks 28 and 32)**

The following procedures/assessments will be performed at visits 10 and 11 (weeks 28 and 32, respectively):

- physical examination symptom directed
- clinical laboratory tests
- anti-dsDNA Ab, C3, and C4 only
- anti-IPP-201101 Ab (visit 10 [week 28])
- vital signs measurements (includes systolic and diastolic blood pressures, pulse, and temperature)
- urine pregnancy test on all women regardless of childbearing potential
- concomitant medication review
- adverse event inquiry
- SLEDAI-2K
- BILAG-2004
- 28-joint count examination for pain and tenderness
- SFI
- PhGA
- C-SSRS Since Last Visit version
- access eCRF page for treatment allocation.
- study drug administration after all assessments have been completed. (Patients should be monitored, at the discretion of the investigator, for at least 1 hour after study drug administration.)

In addition, a blood sample (5 mL) will be obtained for measurement of IPP-201101 plasma concentration prior to and 5 minutes and 1, 2, and 24 hours after study drug administration at visit 11 (week 32) from patients at selected North American and Western European study centers. The actual dates and times of study drug administration and the date and time of sampling will be recorded on the CRF.

### **3.11.3.8 Visit 12 (Week 36)**

The following procedures/assessments will be performed at visit 12 (week 36):

- physical examination symptom directed
- clinical laboratory tests
- ANA
- anti-dsDNA Ab, C3, and C4
- anti-U1-70K snRNP Ab, anti-Sm Ab, CRP, IgG, IgM, IgE, IgA
- anti-IPP-201101 Ab
- vital signs measurements (includes systolic and diastolic blood pressures, pulse, and

- temperature)
- urine pregnancy test on all women regardless of childbearing potential
- concomitant medication review
- adverse event inquiry
- SLEDAI-2K
- BILAG-2004
- 28-joint count examination for pain and tenderness
- SFI
- SF-36
- PhGA
- FACIT-Fatigue
- C-SSRS Since Last Visit version
- Access eCRF page for treatment allocation.
- study drug administration after all assessments have been completed. (Patients should be monitored, at the discretion of the investigator, for at least 1 hour after study drug administration.)

### **3.11.3.9 Visits 13, 14, and 15 (Weeks 40, 44, and 48)**

The following procedures/assessments will be performed at visits 13, 14, and 15 (weeks 40, 44, and 48 respectively):

- physical examination symptom directed
- clinical laboratory tests
- anti-dsDNA Ab, C3, and C4 only
- anti-IPP-201101 Ab (visit 14 [week 44])
- vital signs measurements (includes systolic and diastolic blood pressures, pulse, and temperature)
- urine pregnancy test on all women regardless of childbearing potential
- concomitant medication review (NOTE: Background therapies for SLE may not change from week 44 to week 52.)
- adverse event inquiry
- SLEDAI-2K
- BILAG-2004
- 28-joint count examination for pain and tenderness
- SFI
- PhGA
- C-SSRS Since Last Visit version
- In vitro intracellular and secreted cytokine at Visit 48
- access eCRF page for treatment allocation.

Study drug administration after all assessments have been completed. (Patients should be monitored, at the discretion of the investigator, for at least 1 hour after study drug administration.)

#### **3.11.4 Procedures After Study Drug Treatment (Visit 16/Week 52)**

Patients who participate in the study in compliance with the protocol for at least 48 weeks of treatment will be considered to have completed the study. Patients who complete all study visits will be eligible for participation in a open-label study to assess the continued effectiveness and safety of IPP-201101 treatment.

If a patient is withdrawn from the study before completion of 48 weeks of study drug treatment, final evaluations will be performed at the last visit. To be evaluable for efficacy, a patient must be treated with at least 1 dose of study drug and must have all components of the SRI (baseline SLEDAI-2K total score, BILAG-2004 body system scores, and PhGA score) available. Patients with ongoing adverse events or clinically significant abnormal laboratory test results (as interpreted by the investigator) will be monitored as described in section 7.1.2 and section 7.2, respectively.

If a patient withdraws from the study during the treatment period, the reason must be determined and recorded on the patient's CRF (see section 4.3). For patients who withdraw consent, every attempt will be made to determine the reason. A blood sample for measurement of the concentration of IPP-201101 will be obtained from all patients who have an adverse event leading to withdrawal from the study and/or all patients who have a serious adverse event.

For patients who complete the study, final evaluations will be performed at visit 16 (week 52). For patients who withdraw prematurely from the study before completion of 48 weeks of study drug treatment, final evaluations will be performed at the last visit. The following procedures will be performed at visit 16 (week 52) or at early termination (before completion of the 48 weeks of study drug treatment), if applicable:

- physical examination
- clinical laboratory tests
- ANA
- anti-dsDNA Ab, C3, and C4
- anti-U1-70K snRNP Ab, anti-Sm Ab, CRP, IgG, IgM, IgE, IgA
- anti-IPP-201101 Ab (NOTE: Any patient with a positive test result for anti-IPP-201101 Ab at the final study visit will be followed with additional immunogenicity testing at 8-week intervals until the level returns to baseline value or the levels are judged by the investigator to be chronic, or the patient is lost to follow-up)
- vital signs measurements (includes systolic and diastolic blood pressures, pulse, and temperature)
- urine pregnancy test on all women regardless of childbearing potential
- 12-lead ECG
- concomitant medication review
- adverse event inquiry

- SLEDAI-2K
- BILAG-2004
- 28-joint count examination for pain and tenderness
- SFI
- SDI
- SF-36
- PhGA
- FACIT-Fatigue
- C-SSRS Since Last Visit version
- access IRT to record final patient disposition

## 4 SELECTION AND WITHDRAWAL OF PATIENTS

### 4.1 Patient Inclusion Criteria

Patients are included in the study if all of the following criteria are met:

- (a) The patient is a man or woman between 18 and 70 years of age with an established diagnosis of SLE as defined by ACR Classification Revised Criteria. The diagnosis is fulfilled provided that at least 4 criteria are met.
- (b) The patient has a positive test result for ANA at screening (titer must be at least 1:80 [by human epithelial cell tumor line (HEp-2) ANA assay]) **and/or** a positive test result for anti-dsDNA Ab at screening (value must be 30 IU/mL or more by enzyme-linked immunosorbent assay [ELISA]).
- (c) Written informed consent is obtained.
- (d) Women must be surgically sterile, 2 years postmenopausal, or, if of childbearing potential, using a medically accepted method of contraception, and must agree to continued use of this method for the duration of the study and for 30 days after discontinuation of study drug treatment. Acceptable methods of contraception include barrier method with spermicide, abstinence (when this is in line with the preferred and usual lifestyle of the subject), intrauterine device (IUD), or steroidal contraceptive (oral, transdermal, implanted, and injected) in conjunction with a barrier method.
- (e) The patient has a SLEDAI-2K clinical score of at least 6 points **during screening**. A SLEDAI-2K clinical score is the calculated score without inclusion of the points that may be contributed by having a positive titer for anti-dsDNA Ab or decreased serum complement levels.
- (f) The patient does not have an “A” score on the BILAG-2004 scale.
- (g) If the patient is using oral corticosteroids, the weekly cumulative dose must not exceed 80 mg of prednisone equivalent; the weekly dose must be stable over the 4 weeks preceding the 1st dose of study drug.
- (h) If the patient is using antimalarials, methotrexate, leflunomide, MMF, or azathioprine, the start date must be at least 3 months prior to the 1st dose of study drug, and the daily dose

must be stable over the 4 weeks preceding the 1st dose of study drug.

- (i) If the patient is not currently using corticosteroids, antimalarials, methotrexate, MMF, or azathioprine, the last dose (in case of previous use) must be at least 4 weeks prior to the 1st dose of study drug. For leflunomide, the stop date must be at least 8 weeks before the 1st dose of study drug, unless an adequate cholestyramine washout has been performed. If cholestyramine washout is performed, the last use of leflunomide must be at least 4 weeks before the 1st dose of study drug.

The patient must be willing and able to comply with study restrictions, to remain at the study center for the required duration during each study visit, and to return to the study center for the final assessment as specified in this protocol.

#### **4.2 Patient Exclusion Criteria**

Patients are excluded from participating in this study if 1 or more of the following criteria are met:

- (a) The patient has been treated with intramuscular or intravenous (iv) pulse steroids (ie, 250 to 1000 mg iv total daily dose of methylprednisolone) within 4 weeks of the 1st dose of study drug. The use of intra-articular steroids may be allowed after consultation with the medical expert.
- (b) The patient has received tacrolimus, cyclosporin A, or iv immunoglobulins (IVIG) within 3 months of the 1st dose of study drug.
- (c) The patient has received cyclophosphamide within 6 months prior to the 1st dose of study drug.
- (d) The patient has been treated for SLE with agents such as fusion proteins, therapeutic proteins, or monoclonal antibodies or antibody fragments, within 6 months of the 1st dose of study drug.
- (e) The patient has received B-cell depleting agents such as rituximab, belimumab or epratuzumab within one year of the 1st dose of study drug and has not yet normalized the B-cell count (ie, CD20+ B-cell count is less than normal range and the absolute lymphocyte count [ALC] is less than normal range).
- (f) The patient has New York Heart Association (NYHA) Class III or IV congestive heart failure.
- (g) The patient has an estimated glomerular filtration rate (eGFR) of less than 30 mL/min/1.73 m^2 (via Modification of Diet in Renal Disease [MDRD] equation).
- (h) The patient has an aspartate aminotransferase (AST) or alanine aminotransferase (ALT) value greater than 2 times the upper limit of the normal range (ULN) or a total bilirubin level greater than 1.5 times ULN.
- (i) The patient has a planned immunization with a live or live attenuated vaccine within 3 months prior to administration of the 1st dose of study drug and for 3 months after administration of the last dose of study drug.
- (j) The patient has any clinically significant abnormalities on ECG that are not related to SLE, as determined by the investigator. Patients with stable ECG changes without evidence of active cardiovascular disease may participate at the discretion of the investigator and

medical monitor.

- (k) The patient has an ongoing active systemic infection requiring treatment or a history of severe infection, such as hepatitis or pneumonia, in the 3 months prior to administration of the 1st dose of study drug. Less severe infections in the 3 months prior to administration of the 1st dose of study drug are permitted at the discretion of the investigator and medical monitor.
- (l) The patient has any concomitant medical condition unrelated to SLE that may interfere with his or her safety or with evaluation of the study drug, as determined by the investigator.
- (m) The patient has a history of a medical condition other than SLE that has required treatment with oral corticosteroids in excess of 80 mg of prednisone equivalent/week within 3 months of the 1st dose of study drug.
- (n) The patient has a positive test result for HBsAg or HCV Ab.
- (o) The patient has a known positive history of antibodies to human immunodeficiency virus (HIV) or HIV disease or other immunosuppressive state (eg, agammaglobulinemia, etc).
- (p) The patient has a history of alcohol or substance dependence or abuse (with the exception of nicotine), according to the Diagnostic and Statistical Manual of Mental Disorders of the American Psychiatric Association, Fourth Edition, Text Revision (DSM-IV-TR), within 3 months of the screening visit or has current substance abuse.
- (q) The patient has a history of severe allergic reactions to or hypersensitivity to any component of the study drug or placebo.
- (r) The patient has undergone or is undergoing treatment with another investigational drug for the treatment of lupus within 6 months prior to the 1st dose of study drug or has received any other investigational drug for any other condition within 4 weeks prior to the 1st dose of study drug.
- (s) The patient has previously participated in a clinical study with IPP-201101.
- (t) The patient is a pregnant or lactating woman. (Any women becoming pregnant during the study will be withdrawn from the study.)
- (u) The patient is unlikely to comply with the study protocol or is unsuitable for any other reason, as judged by the investigator or medical monitor.

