- an inability to reduce corticosteroid dose to the baseline dose or to withdraw therapy if the patient required a temporary increase in corticosteroid dose or a short course of corticosteroid treatment (ie, 2 weeks) and the medication is unable to be tapered to the baseline dose or be withdrawn, respectively
- therapy is initiated with pulse iv steroids
- an increase in the baseline dose of immunosuppressive agents (methotrexate, azathioprine, MMF)
- initiation of new immunosuppressive therapy (cyclophosphamide, methotrexate, azathioprine, cyclosporin, tacrolimus, leflunomide, MMF)
- initiation of therapy with biologics for the treatment of SLE
- any change in the doses of background therapies beginning with week 44 (visit 14) More information is provided in section 3.6 and Appendix B.

Patients will be excluded from participation in the study for any of the following reasons:

- they have been treated with iv pulse steroids within 4 weeks of the 1st dose of study drug
- they have received tacrolimus, cyclosporin A, or IVIG within 3 months of the 1st dose of study drug
- they have received cyclophosphamide or have been treated with biologic agents for SLE, such as fusion proteins, therapeutic proteins, or monoclonal antibodies or antibody fragments, within 6 months of the 1st dose of study drug
- they have received B-cell depleting agents such as rituximab or belimumab within one year of 1st dose of study drug and have not yet normalized the B-cell count
- they have a planned immunization with a live or live attenuated vaccine within 3 months prior to administration of the 1st dose of study drug and for 3 months after the last dose of study drug is administered

More information is provided in section 4.2 and Appendix B.

At each study center visit after the screening visit, the investigator will ask the patient whether any medications (other than study drug), including over-the-counter (OTC) medications, were taken since the previous visit (see Appendix B).

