**APPENDIX B**  
**CONCOMITANT SYSTEMIC LUPUS ERYTHEMATOSUS**  
**MEDICATIONS**

(Sample provided in this appendix is for reference only.)

Concomitant Systemic Lupus Erythematosus Medicationsa			
	Stop date	Stable date	Medication
			Start date
DMARDS/immunosuppressantsb			
Antimalarials			
Hydroxychloroquine sulfate	3 months prior to 1 st dose	4 weeks prior to 1 st dose	4 weeks prior to 1 st dose
Chloroquine			
Methotrexate	3 months prior to 1 st dose	4 weeks prior to 1 st dose	4 weeks prior to 1 st dose
Leflunomide	3 months prior to 1 st dose	8 weeks prior to 1 st dose unless an adequate cholestyramine washout has been completed. c If cholestyramine washout is performed, the last use of leflunomide must be at least 4 weeks before the 1 st dose of study drug.	4 weeks prior to 1 st dose
Mycophenolate mofetil	3 months prior to 1 st dose	4 weeks prior to 1 st dose	4 weeks prior to 1 st dose
Azathioprine	3 months prior to 1 st dose	4 weeks prior to 1 st dose	4 weeks prior to 1 st dose
Steroids			
Prednisone or prednisolone (most likely to be used)	NA	NA	4 weeks prior to 1 st dose

a Changes in background therapies, including use of steroids, should not occur after week 44.

b Dosages of these medications should remain stable during the study. Patients will be withdrawn from the study if there is an increase in the dose of immunosuppressive agents (methotrexate, azathioprine, mycophenolate mofetil [MMF], leflunomide) above the baseline level or if any new immunosuppressive agents are introduced.

c Cholestyramine washout (per ARAVA package insert) is 8 grams administered 3 times daily for 11 days (days do not need to be consecutive). Compliance for this washout is low. DMARDS=disease-modifying antirheumatic drugs; NA=not applicable.

Excluded medicationsa	Must stop by:
iv pulse steroids (methylprednisolone)	>4 weeks prior to 1 st dose
Tacrolimus	>3 months prior to 1 st dose
Cyclosporin A therapy)	>3 months prior to 1 st dose >3 months prior to 1 st dose
Cyclophosphamide	>6 months prior to 1 st dose
Biologic agents	>6 months prior to 1 st dose

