Fusion proteins (eg, atacicept, abatacept, etanercept)	
Therapeutic proteins	
Monoclonal antibodies b (eg, ocrelizumab, alemtuzumab, rituximab, epratuzumab, belimumab)	
B-cell depleting agents b (eg, rituximab, epratuzumab, belimumab)	B-cell count and ALC $\geq$ normal ranges >3 months prior to 1 st dose a
Live or live-attenuated vaccines (eg, nasal flu vaccine; measles, mumps and rubella vaccine; oral polio vaccine, etc.)	
Investigational drug for the treatment of lupus	>6 months prior to 1 st dose
Investigational drug for the treatment of a condition other than lupus	>4 weeks prior to 1 st dose

a Patients will be withdrawn from the study if there is an initiation of new immunosuppressive therapy (eg, cyclophosphamide, cyclosporin, tacrolimus) or if there is an initiation of therapy with biologics for the treatment of systemic lupus erythematosus (SLE).

b For B-cell depleting agents that are also monoclonal antibodies, the most conservative restriction applies. iv=intravenous; IVIG=intravenous immunoglobulin; ALC=absolute lymphocyte count.

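### Exclusion 4.2(e) and synopsis (e) require both a low CD20+ count and a low ALC, so a patient with a low CD20+ count and a normal ALC is not excluded, contrary to Appendix B

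*Protocol*

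**What the plan says.** - **Section 4.2(e) and synopsis (e), lead-in.** A patient who received a B-cell depleting agent within one year of the first dose is excluded if he or she "has not yet normalized the B-cell count".
- **Section 4.2(e) and synopsis (e), bracket.** Introduced by *ie*, the same bracket in both places defines that state: the CD20+ "B-cell count is less than normal range and the absolute lymphocyte count [ALC] is less than normal range".
- **Section 5.2.** The rule is repeated for patients who "have not yet normalized the B-cell count", with no mention of ALC. The list closes with "More information is provided in section 4.2 and Appendix B".
- **Appendix B, excluded-medications table.** The entry for B-cell depleting agents is "B-cell count and ALC $\geq$ normal ranges". A footnote adds: "For B-cell depleting agents that are also monoclonal antibodies, the most conservative restriction applies". The appendix is headed "Sample provided in this appendix is for reference only".
- **Section 4.2(d).** A separate 6-month bar covers the following: "The patient has been treated for SLE with agents such as fusion proteins, therapeutic proteins, or monoclonal antibodies or antibody fragments".

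**The concern.** The purpose of (e) is to keep out patients whose B cells have not recovered from a depleting agent. As written, a normal total lymphocyte count is enough to clear a patient whose CD20+ count is still low, although the CD20+ count is the quantity the criterion names.

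Two things are at stake. One is the entry of still-depleted patients into a trial of an immunomodulatory peptide, through what looks like a slip in wording. The other is consistency: about 50 centers could give different answers for the same patient, depending on whether they follow the bracket or Appendix B. Under section 12.1.2, a patient found not to meet eligibility is a protocol violation and is normally discontinued. It should therefore be clear which patients those are.

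**Working it through.** The plan states no figure here, and no sample size, power or alpha enters. The check is logical. Take a patient given a B-cell depleting agent within one year and cross CD20+ (low or normal) with ALC (low or normal).

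**Rules**

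- Bracket in 4.2(e) and synopsis (e): excluded if CD20+ low AND ALC low.
- Lead-in of (e), in its plain sense, and section 5.2: excluded if CD20+ low.
- Appendix B: entry requires CD20+ at or above normal AND ALC at or above normal. The negation is: excluded if CD20+ low OR ALC low.

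| CD20+ / ALC | Bracket | Lead-in and 5.2 | Appendix B |
|---|---|---|---|
| low / low | excluded | excluded | excluded |
| low / normal | **not excluded** | excluded | excluded |
| normal / low | not excluded | not excluded | excluded |
| normal / normal | not excluded | not excluded | not excluded |

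**Reading the table**

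- Bracket against lead-in: they differ in 1 of 4 cells (low/normal).
- Bracket against Appendix B: they differ in 2 of 4 cells (low/normal and normal/low).
- The point rests on low/normal, where only the bracket lets the patient through.
- In normal/low, Appendix B stands alone against both other sources, so the documents do not settle what was intended there.

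**Time window.** For antibodies given for SLE, exclusion (d) bars the first 6 months whatever the counts. Criterion (e) runs to 12 months, so 12 − 6 = 6 months depend on (e) alone, namely months 6 to 12.

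**Effect of the two possible rewordings**

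| Reworded bracket | Cells changed from the present bracket | Agreement |
|---|---|---|
| CD20+ low OR ALC low | 2 of 4 | with Appendix B as it stands, 4 of 4 |
| CD20+ low, ALC dropped | 1 of 4 | with lead-in and 5.2, 4 of 4; with Appendix B, 4 of 4 only if ALC is dropped there too |

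Both close the low/normal cell.

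**Tests available.** Lymphocytes are in the hematology panel (section 7.2.2). No CD20+ count appears in Table 2, in the visit 1 list (section 3.11.1) or in sections 7.2.1 to 7.2.4. Under the present bracket a normal ALC therefore settles (e) without any CD20+ result.

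The Appendix B table is broken in the text available. A limit of more than 3 months on the same line probably belongs to the live-vaccine row and is not used here.

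**The case against.** **The lead-in sets no threshold of its own.** The word *ie* introduces its definition, and section 5.2 is shorthand that points back to 4.2 and Appendix B. That is fair: section 5.2 should not be counted as a separate rule, and the one independently worded rule in conflict is Appendix B. But Appendix B is labelled as a reference sample, so it does not override the numbered criterion. A definition that clears a patient with a low B-cell count also remains at odds with the ordinary meaning of the words it defines.

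**Other criteria cover the gap.** Exclusion (d) does so only for 6 months and only for treatment of SLE. Exclusion (u), and possibly (o), allow a site to refuse a patient, but by judgement. They do not repair an objective rule.

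**The safety argument is thin.** Much of this stands. Section 1.4 says data on the peptide's long-term effect on immune competence are insufficient; it does not speak about entering B-cell-depleted patients. Criterion (e) also lapses after one year, and background immunosuppressants are allowed. A reader might infer that the protocol treats B-cell depletion as an absolute bar and that the bracket breaches it. The documents do not support that.

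**ALC should simply be deleted, and *or* would be wrong.** A reader might infer this because *or* would exclude patients with a normal CD20+ count and a low ALC, and a low ALC may reflect the lupus. The documents do not settle it. Appendix B already excludes those patients, and its footnote favours the stricter restriction. Lymphocytes are an item of BILAG-2004 (Appendix D, item 93), but the protocol nowhere says that a low ALC should be disregarded at entry.

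**Conclusion.** The point holds as a wording error in a numbered exclusion criterion, present in two places. Followed literally, (e) lets through a recently treated patient with a low CD20+ count and a normal ALC, whom Appendix B and the plain sense of the lead-in and section 5.2 would refuse.

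The size is small. The count of 1 cell in 4 describes logical combinations and is not a frequency. The protocol gives no number of patients in that cell, and it is probably low. A reader might infer that the slip threatens the primary comparison. Nothing in the document supports that, since eligibility is applied before blinded 1:1 randomization, and no effect on bias, power or alpha is claimed. This is a worthwhile correction of low severity. It rests on reading *ie* and *and* as written, and on Appendix B not overriding section 4.2.

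**What to change.** 1. Reword the bracket in 4.2(e) and synopsis (e) so that a low CD20+ count excludes regardless of ALC.
2. Make the Appendix B entry state the same rule.
3. Have the sponsor decide whether a low ALC with a normal CD20+ count also excludes. Replacing *and* with *or* in the bracket matches Appendix B as written. Deleting ALC from the bracket matches the lead-in and section 5.2, but ALC must then also come out of Appendix B, which removes a restriction now stated there.

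The edit is a few words in up to three places, with possibly a few more screen failures. It may also mean extra testing: patients treated within one year who can now be cleared on a normal ALC alone would need a CD20+ count. Criterion (e) already presupposes that test, but the protocol's listed tests do not include it, so the amendment should say where the result comes from.
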